7.2. Analysis Populations

Since there will be no flortaucipir F 18 dose in this study, there will be no safety evaluation planned thus the analysis population will be for efficacy analyses only.

Efficacy analysis population will include all valid scan reading results from 5 readers on 242 cases. Valid images will be considered unevaluable only if 3 out of 5 independent readers declare the image unevaluable for the same reason. Subjects with invalid or unevaluable PET data will be excluded from efficacy analyses. Criteria for declaring an image invalid or not evaluable will be specified in advance in the Image Review Charter.

7.2.1. Efficacy Analysis Population for Accuracy Evaluation (EFFA)

The EFFA will include reading results for all valid and interpretable scans from all 83 autopsy cases from study A16. The analysis set will be used to conduct the primary objective #1 efficacy analyses #1 and #2 (refer to Section 10.3.1 and 10.3.2), and secondary objective #1 analysis #1 and #2 (refer to section 10.4.1).

For scans that will be read twice for intra-reader reliability evaluation, the first read will be included in the EFFA.

Sixteen cases enrolled as supplementary academic center (SAC) autopsy cases only had neuropathologist diagnosis from one hemisphere. Therefore, the visual reads from the corresponding side will be used in the primary objective analyses where the accuracy of τ AD visual reads is assessed, since the τ AD visual read data is available from both sides of the brain. For secondary objective analyses where the accuracy of τ AD++ visual reads is assessed, the τ AD++ read for the whole brain will be used due to data availability.

7.2.2. Efficacy Analysis Population for Precision Evaluation (EFFP)

The EFFP are defined according to analyses, as below:

7.2.2.1. EFP1

EFP1 will include reading results for all valid and interpretable scans from all 242 cases from studies A16 and A05. The analysis set will be used to conduct primary objective #2 efficacy analysis (refer to Section 10.3.3), and secondary objective #2 efficacy analysis (refer to section 10.4.2).

For scans that will be read twice for intra-reader reliability evaluation, the first read will be included in the EFP1. For the 16 SAC cases, the overall visual interpretation based on whole brain will be used.

7.2.2.2. EFP2

EFP2 will include reading results for all valid and interpretable scans from the 159 cases from study A05. The analysis set will be used to conduct analysis for secondary objective #3 (refer to Section 10.4.3).

For scans that will be read twice for intra-reader reliability evaluation, the first read will be included in the EFP2.

7.2.2.3. EFP3

EFP3 will include reading results for all valid and interpretable scans from the 20 cases randomly selected to evaluate intra-reader reliability. The analysis set will be used to conduct efficacy analysis for secondary objective #4 (refer to Section 10.4.4). For the 16 SAC cases, the overall visual interpretation based on whole brain will be used.

8. DATA PRESENTATIONS AND DATA MANAGEMENT

8.1. Data Presentations

The data will be presented with tables and listings in the following categories:

1. Demographic profile for the study participants
2. Analyses of the primary, secondary and exploratory efficacy data

8.2. Data Management

The data will be collected using an electronic case report form (eCRF) system that was developed by data vendor American College of Radiology (ACR). There will be an edit check and quality control before the database lock to ensure the highest possible quality of the study data.

Derived working datasets will be created using the Statistical Analysis System (SAS) software. Data analyses and summary tables will be generated using SAS version 9.0 or higher.

8.3. General Post Text Summary

8.3.1. Table and Individual Patient Data Listing Format Considerations

The tables and listings will be numbered using a decimal system to reflect main levels of unique tables and listings and sub-levels of replicate tables and the listings with two digits per level (e.g., Table XX.YY.ZZ...). Tables will be presented in Appendix 14 and individual patient data listings are presented in Appendix 16.

9. BASELINE PATIENT DATA AND EFFICACY ENDPOINT

9.1. Demographic, PET Scan, and Autopsy Data

The baseline data will be carried forward from the previous studies ¹⁸F-AV-1451-A05 and ¹⁸F-AV-1451-A16, which include the following:

- Demographics: age, gender, race, and ethnicity
- PET scan and autopsy information:
Date of flortaucipir PET scan, date of autopsy, and Interval between image and autopsy.

9.2. Neuropathological Evaluation

All neuropathological measurements on brain tissue will be obtained from study A16, which were evaluated in a standardized fashion in a qualified laboratory.

Neuropathological assessment was derived from the NIA-AA guidelines (Hyman et al., 2012). The truth standard (TS) for primary objective #1 efficacy analysis #1 was constructed from NFT scores at autopsy as shown in Table 2.

Table 2. Autopsy NFT Score Truth Standard

Braak Stage	NFT Score ^A	Truth Standard
0 (no NFTs)	B0	
I-II	B1	Negative
III-IV	B2	
V-VI	B3	Positive

^AAdapted from Hyman et al., 2012.

The TS for primary objective #1 efficacy analysis #2 was constructed from levels of AD neuropathological change as shown in Table 3.

Table 3. NIA-AA Autopsy Diagnosis Level of AD Neuropathological Change Truth Standard

Level of AD Neuropathological Change	Truth Standard
Present ^A	
None	
Low	Negative
Intermediate	
High	Positive

^AAdapted from Hyman et al., 2012.

9.3. Flortaucipir F 18 PET Imaging Evaluation

Criteria for declaring an image invalid or not evaluable were specified in advance in the Image Review Charter. In this SAP, valid images will be considered as unevaluable only if at least 3 out of 5 independent readers declare the image unevaluable for the same reason(s).

Flortaucipir F 18 PET images will be interpreted by visual examination using the following criteria:

Read Outcome		Objective Image Features
Not consistent with AD pattern (τAD-)		No increased neocortical activity, or increased neocortical activity isolated to the mesial temporal, anterolateral temporal, and/or frontal regions.
AD pattern (τAD)	τAD+	In either hemisphere, increased neocortical activity in the posterolateral temporal (PLT) or occipital region(s).
	τAD++	In either hemisphere, increased neocortical activity in the parietal/precuneus region(s), or frontal region(s) with increased uptake in the PLT, parietal, or occipital region(s).

For the purpose of testing primary objective #1, a scan interpretation will be considered positive (hypothesized to correspond to a B3 NFT score for primary objective #1 efficacy analysis 1 and an NIA-AA score of high AD pathology for primary objective #1 efficacy analysis #2) if the scan was interpreted as at least consistent with an AD pattern (τAD+ or τAD++).

For the purpose of testing secondary objective #1, a scan interpretation will be considered positive (hypothesized to correspond to a B3 NFT score for secondary objective #1 efficacy analysis #1 and an NIA-AA score of high AD pathology for secondary objective #1 efficacy analysis #2) if the scan was interpreted as τAD++.

10. EFFICACY ANALYSIS

10.1. General Considerations

Categorical variables will be summarized as frequencies and percentages by enrolling diagnostic group (Dementia, MCI, or CN). Continuous variables will be summarized using descriptive statistics (n, mean, median, standard deviation, minimum and maximum) by each diagnostic group.

All inferential statistics will be performed at the 2-sided, 0.05 level of significance.

SAS Version 9.0 or above will be used to perform all analyses.

10.2. Multiple comparisons/multiplicity of hypotheses testing

Three hypotheses will be tested for the two co-primary objectives, as detailed in section 10.3. This trial will be considered successful if all three primary efficacy analyses achieve their success criteria.

10.3. Analyses of the Primary Objectives

10.3.1. Primary Objective #1 Efficacy Analysis 1: Accuracy of Flortaucipir F 18 PET Scan Interpreted as AD Pattern in Detecting NFT Tau Stage

The first primary analysis will evaluate the accuracy of flortaucipir F 18 PET scan in detecting neurofibrillary tangle as measured by NFT stage (truth standard), as detailed in Table 1 of section 9.2. The hypothesis to be tested is that for at least the same 3 out of 5 independent readers, the lower bound of the two-sided 95% CI for both sensitivity and specificity of flortaucipir PET reading interpretations will be $\geq 50\%$.

This analysis will be based on the EFFA, as defined in 7.2.1.

The following table contains terms used to define sensitivity, specificity, accuracy, positive predictive value (PPV), negative predictive value (NPV), likelihood ratio positive (LR+) and likelihood ratio negative (LR-):

Diagnostic Test: Flortaucipir F 18 PET Scan Read Result	Truth Standard	
	NFT B3	NFT B0-B2
Positive: Flortaucipir F 18 neocortical uptake; AD pattern (τ AD+, τ AD++)	True Positive (TP)	False Positive (FP)
Negative: Flortaucipir F 18 neocortical uptake; not consistent with AD pattern (τ AD-)	False Negative (FN)	True Negative (TN)

The sensitivity, which evaluates how good a test is at detecting a positive disease, will be calculated as:

$$100 \times \frac{TP}{TP + FN}$$

The specificity, which estimates how likely subjects without the disease can be correctly ruled out, will be calculated as:

$$100 \times \frac{TN}{FP + TN}$$

The accuracy, which evaluates the overall proportion of observed agreement, will be calculated as:

$$100 \times \frac{TP + TN}{TP + FN + FP + TN}$$

The PPV, which is the proportion of positive test results that are true positives, will be calculated as:

$$100 \times \frac{TP}{TP + FP}$$

The NPV, which is the proportion of subjects with a negative test result who are correctly diagnosed, will be calculated as:

$$100 \times \frac{TN}{FN + TN}$$

The 95% CIs provided for specificity, sensitivity, accuracy, PPV and NPV will be based on the Wilson score method (Wilson 1927; Newcombe 1998).

The LR+, which is true positive rate divided by the false positive rate, will be calculated as:

$$\frac{\text{sensitivity}}{1 - \text{specificity}}$$

The LR-, which is the false negative rate divided by the true negative rate, will be calculated as:

$$\frac{1 - \text{sensitivity}}{\text{specificity}}$$

10.3.2. Primary Objective #1 Efficacy Analysis #2: Accuracy of Flortaucipir F 18 PET Scan Interpreted as AD Pattern in Detecting AD Neuropathological Change

This analysis will evaluate the accuracy of flortaucipir F 18 PET scan in detecting High AD neuropathological change (ADNC), as detailed in Table 2 of section 9.2. Like primary analysis #1, the hypothesis to be tested is that for at least the same 3 out of 5 independent readers, the lower bound of the two-sided 95% CI for both sensitivity and specificity of flortaucipir PET reading interpretations will be $\geq 50\%$.

This analysis will be based on the EFFA, as defined in 7.2.1.

The calculation of sensitivity, specificity, NPV, PPV, LR+ and LR- analyses, as well as the confidence interval calculation will be identical to primary analysis #1, with ADNC as TS.

10.3.3. Primary Objective #2 Efficacy Analysis: Inter-Reader Agreement of Flortaucipir F 18 PET Scan Interpreted as AD Pattern

The overall reader to reader reliability across 5 readers for interpreting the flortaucipir PET scan will be assessed using Fleiss’ Kappa. The primary hypothesis to be tested is that the lower bound of two-sided 95% confidence interval of Fleiss’ Kappa will be greater than or equal to 0.6. This analysis will be based on the EFFP1, as defined in 7.2.2.1.

The degree of agreement between two readers for the interpretation of flortaucipir PET scan will be assessed in a pair-wise manner using Cohen’s Kappa statistics.

The percent of agreement between the two readers will be calculated for each reader pair. The over percent of agreement across 5 readers will be calculated too. All these results will be summarized in tables.

10.4. Analysis of Secondary Objectives

10.4.1. Test the Relationship Between Ante-mortem Flortaucipir F 18 PET Imaging of an AD Pattern with Uptake Beyond the Temporal/Occipital Regions (τ AD++) and Tau Neurofibrillary Pathology Associated with AD, as Measured at Autopsy

To further evaluation the diagnostic performance of flortaucipir scans, the same scan interpretation from the readers will be reclassified as an AD pattern with uptake beyond the temporal/occipital regions (τ AD++: positive) vs. otherwise (τ AD+/ τ AD-: negative) and compared to the TS as detailed in section 9.2. That is, calculating the diagnostic performance statistics following the tables as below:

Secondary Objective #1 Efficacy Analysis #1

Diagnostic Test: Flortaucipir F 18 PET Scan Read Result	Truth Standard	
	NFT Score B3 [Truth Positive]	NFT Score B0–B2 [Truth Negative]
Positive: Flortaucipir F 18 neocortical uptake; τ AD++ pattern	True Positive (TP)	False Positive (FP)
Negative: Flortaucipir F 18 neocortical uptake; non- τ AD++ pattern (τ AD-/ τ AD+)	False Negative (FN)	True Negative (TN)

And:

Secondary Objective #1 Efficacy Analysis #2

Diagnostic Test: Flortaucipir F 18 PET Scan Read Result	Truth Standard	
	High AD Neuropathologic Change [Truth Positive]	Not, Low, or Intermediate AD Neuropathologic Change [Truth Negative]
Positive: Flortaucipir F 18 neocortical uptake; τ AD++ pattern	True Positive (TP)	False Positive (FP)
Negative: Flortaucipir F 18 neocortical uptake; non- τ AD++ pattern (τ AD-/ τ AD+)	False Negative (FN)	True Negative (TN)

The calculation of sensitivity, specificity, NPV, PPV, LR+, LR-, as well as the associate 95% CI will be the same as described in section 10.3.1.

10.4.2. Inter-Reader Reliability of Flortaucipir F 18 PET Scan Interpreted as τ AD++ Pattern

This analysis will assess the reliability of flortaucipir F 18 scan interpreted as τ AD++ pattern across 5 readers. Same as analysis described in section 10.3.3, Fleiss' Kappa and the associated two-sided 95% CI will be calculated. The hypothesis to be tested is that the lower bound of two-sided 95% confidence interval of Fleiss' Kappa will be greater than or equal to 0.6. This analysis will be based on the EFP1, as defined in 7.2.2.1.

10.4.3. Inter-Reader Agreement of Flortaucipir F 18 PET Scan Interpreted as AD Pattern for Intended Clinical Use Population

The subjects enrolled in study A05 were representative cases of the intended clinical use population for flortaucipir F 18 scan. This analysis will evaluate the inter-reader reliability of flortaucipir scan interpreted as AD pattern with this intended clinical practice population. Analyses similar to 10.3.3 will be conducted using EFP2, which will be based on 159 A05 cases as defined in 7.2.2.2.

10.4.4. Intra-Reader Agreement of Flortaucipir F 18 PET Scan Visual Interpretation Interpreted as AD Pattern

Intra-reader reliability will be assessed using randomly selected 20 cases (EFP3) as defined in section 7.2.2.3. These randomly selected cases will be read twice by every reader. A Cohen's Kappa statistics will be used to assess the agreement of the two reading results (scans that are interpreted as an AD pattern, i.e., τ AD (τ AD+/ τ AD++) vs τ AD-) by every reader.

The percent of agreement between the two readings from same reader will be calculated for each reader. All these results will be summarized in tables.

10.5. Other Efficacy Analyses

10.5.1. Accuracy of Flortaucipir F 18 Scan in Detecting Tau Neurofibrillary Pathology Associated with Alzheimer's Disease (AD), Based on Majority Scan Interpretations

For each image, the majority interpretation of 5 independent readers will be derived using individual readers' interpretation results. Diagnostic performance of this majority interpretation will be assessed relative to the autopsy NFT score TS as per primary objective #1 efficacy analysis #1 (refer to Section **Error! Reference source not found.**0.3.1) and again relative to the NIA-AA autopsy diagnosis TS as per primary objective #1 efficacy analysis #2 (refer to Section **Error! Reference source not found.**0.3.2).

The sensitivity and specificity along with their two-sided 95% CIs (based on the Wilson score method) will be calculated for the majority interpretation of 5 independent readers relative to the appropriate TS.

The accuracy, PPV, NPV, LR+ and LR- of the flortaucipir F 18 PET imaging classification for the majority interpretation of 5 independent readers relative to the appropriate TS will be also calculated. Two-sided 95% CIs (based on the Wilson score method) will be provided for the accuracy, the PPV and NPV.

10.5.2. Inter-Reader Agreement of Flortaucipir F 18 PET Scan Interpreted as AD Pattern for Autopsy Population

The inter-reader agreement analysis across 5 readers of flortaucipir F 18 PET scan interpretation (interpreted as AD pattern) will be repeated based on the EFFA. Fleiss' Kappa, and other statistics, will be calculated the same as described in section 10.3.3.

10.5.3. Additional Visual Interpretation Reliability Assessment of Flortaucipir F 18 Scan Interpreted as τ AD++ Pattern

These additional visual interpretation reliability assessments will be conducted for flortaucipir F 18 scans based on the τ AD++ pattern:

1) Inter-reader reliability for scans including clinical use population only (A05 cases):

Fleiss' Kappa, and other statistics will be calculated the same as described in section 10.3.3., based on EFFP2.

2) Inter-reader reliability for scans including autopsy cases only (A16 cases):

Fleiss' Kappa, and other statistics will be calculated the same as described in section 10.3.3., based on EFFA.

3) Intra-reader reliability for scans included in EFP3:

Cohen’s kappa and other statistics will be calculated the same as described in section 10.4.4, based on EFP3.

10.5.4. Diagnostic Performance Calculation for Flortaucipir F 18 PET Scan Reader Interpretation vs. Modified Autopsy NFT Score TS (B0/1 vs. B2/3)

Flortaucipir F 18 scan visual interpretation, both as described in primary objective #1 analyses and secondary objective #1 analyses will be compared to a modified autopsy NFT score TS, which classifies NFT score B2 and B3 as truth standard positive, and NFT score B0 and B1 as truth standard negative.

The diagnostic performance statistics calculation will be based on the tables as below:

Flortaucipir scan interpretation τ AD pattern (τ AD+/ τ AD++) as scan reads positive:

Diagnostic Test: Flortaucipir F 18 PET Scan Read Result	Modified Truth Standard	
	NFT Score B2/B3 [Truth Positive]	NFT Score B0/B1 [Truth Negative]
Positive: Flortaucipir F 18 neocortical uptake; AD pattern (τ AD+, τ AD++)	True Positive (TP)	False Positive (FP)
Negative: Flortaucipir F 18 neocortical uptake; not consistent with AD pattern (τ AD-)	False Negative (FN)	True Negative (TN)

And τ AD++ pattern as scan reads positive:

Diagnostic Test: Flortaucipir F 18 PET Scan Read Result	Modified Truth Standard	
	NFT Score B2/B3 [Truth Positive]	NFT Score B0/B1 [Truth Negative]
Positive: Flortaucipir F 18 neocortical uptake; τ AD++ pattern	True Positive (TP)	False Positive (FP)
Negative: Flortaucipir F 18 neocortical uptake; non- τ AD++ pattern (τ AD-/ τ AD+)	False Negative (FN)	True Negative (TN)

The calculation of sensitivity, specificity, NPV, PPV, LR+, LR-, as well as the associate 95% CI will be the same as described in section 10.3.1.

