11. SENSITIVITY ANALYSIS

The primary objective analyses will be repeated by using the whole brain visual reads (for τAD pattern) for SAC cases. Identical analyses will be conducted as described in section 10.3.

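### Does SAP 10.5.2 put one-hemisphere SAC reads into the A16 kappa, and does it matter that SAP 11 repeats the primary kappa unchanged?

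*SAP*

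**What the plan says.** The A16-only kappa for the τAD pattern (SAP 10.5.2) "will be repeated based on the EFFA", and its statistics "will be calculated the same as described in section 10.3.3". SAP 10.5.3(2) also names EFFA for the A16-only τAD++ kappa.

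SAP 7.2.1 defines EFFA as the reads of all valid, interpretable scans among the 83 autopsy cases. On its use it says "The analysis set will be used to conduct the primary objective #1 efficacy analyses #1 and #2", and adds the two accuracy analyses of secondary objective 1. For the 16 SAC cases it says that "the visual reads from the corresponding side will be used in the primary objective analyses where the accuracy of" τAD reads is being assessed. For τAD++ accuracy, the "read for the whole brain will be used due to data availability".

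The primary kappa (SAP 10.3.3) runs on the set defined in SAP 7.2.2.1, which states: "For the 16 SAC cases, the overall visual interpretation based on whole brain will be used". Protocol 5.4.1.2 gives the same rule for the primary kappa, and protocol 5.4.2.2 gives it for the τAD++ kappa. Protocol 5.4.2.3 calls the A16-only kappa exploratory and similar to the analysis before it.

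SAP 11 repeats the primary objective analyses with whole-brain τAD reads for SAC cases: "Identical analyses will be conducted as described in section 10.3".

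**The concern.** EFFA is the accuracy set, and its only stated τAD rule for SAC cases is the sampled-side read. The two precision sets that can contain SAC scans, EFP1 and EFP3, each carry an explicit whole-brain rule, and EFFA has no such rule for τAD. A programmer who built EFFA once, with sampled-side reads, and reused it for 10.5.2 would enter one-sided reads for the SAC cases. The A16 τAD kappa would then not be the A16 part of the pooled 242-scan kappa, and it would use a different read unit from the A16 τAD++ kappa.

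The second worry is SAP 11. Section 10.3 includes 10.3.3, so a co-primary endpoint has a listed sensitivity analysis that cannot differ from the primary result. A reader might take the match as evidence of robustness.

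**Working it through.** **1. The plan's own figures.** The counts agree: 3 + 64 + 16 = 83 and 83 + 159 = 242. The stated power for the primary kappa (over 90% for 242 scans, 5 readers, expected kappa 0.7, threshold 0.6, two-sided 0.05) is not in dispute, and it reproduces:

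- Power = Φ(0.1/SE − 1.96).
- Null SE = √(2/(242 × 5 × 4)) = 0.0203, which gives 99.8%.
- Non-null SD from a beta-binomial simulation (kappa 0.7, 56% positive) = 0.0298, which gives Φ(3.36 − 1.96) = 91.9%.
- Direct simulation of the lower-bound rule with a jackknife SE gives 89.8%.

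**2. SAC read level, analysis by analysis.**

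| Analysis | Set | SAC read level | Source |
|---|---|---|---|
| 10.3.1, 10.3.2 τAD accuracy | EFFA | sampled side | SAP 7.2.1 |
| 10.4.1 τAD++ accuracy | EFFA | whole brain | SAP 7.2.1 |
| 10.3.3 primary kappa | EFP1 | whole brain | SAP 7.2.2.1, protocol 5.4.1.2 |
| 10.4.2 τAD++ kappa | EFP1 | whole brain | SAP 7.2.2.1, protocol 5.4.2.2 |
| 10.5.2 A16 τAD kappa | EFFA | not stated; method as 10.3.3 | SAP 10.5.2 |
| 10.5.3(2) A16 τAD++ kappa | EFFA | whole brain, on data availability | SAP 7.2.1 |

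The first two rows show that EFFA has no single read level: the level follows the analysis. The sampled-side rule needs two conditions, a primary objective analysis and an assessment of τAD accuracy. SAP 10.5.2 meets neither. The reason for the rule, one-sided pathology, also has no bearing on reader agreement, which uses no truth standard. The reference to 10.3.3 and the protocol both point to whole-brain reads, so EFFA in 10.5.2 most naturally just selects the 83 A16 scans.

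**3. Size if the other reading were taken.** At most 16/83 = 19.3% of the A16 scans could be affected. By the read criteria, a scan is τAD-positive if either hemisphere shows the pattern, so a one-sided read can only turn a positive into a negative. If SAC cases share the roughly 56% positive rate in SAP 6, about 16 × 0.56 = 9 scans could change at all. The documents give no rate at which a whole-brain positive is negative on the sampled side. For assumed rates, simulated A16 data (83 scans, kappa 0.7, 56% positive, 16 SAC) give these mean shifts in kappa:

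| Assumed rate | Readers change independently | All readers change together on a case |
|---|---|---|
| 5% | −0.015 | +0.004 |
| 10% | −0.027 | +0.007 |
| 20% | −0.047 | +0.014 |

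Under the same model the sampling SD of a kappa on 83 scans is 0.051, so each mean shift is below one SD.

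**4. SAP 11 applied to 10.3.3.** The primary analysis uses 242 scans with 16 SAC cases read on the whole brain, and the repeat uses the same 242 scans and the same reads. The difference in kappa is exactly 0. For 10.3.1 and 10.3.2 the repeat replaces sampled-side with whole-brain reads, so the results can change.

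**The case for a change.** The strongest case for a change is that a final SAP should not let two competent programmers obtain different numbers. In 10.5.2 the named set suggests one read level and the named method another. The whole-brain rule is written out for EFP1 and EFP3, so its absence from EFFA is noticeable. Protocol 5.2.2 plans kappas on all 242 scans, on the 159 A05 scans and on the 83 A16 scans, and these are naturally read together. The wording could be tightened without new data.

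What stands is that the SAC read level in 10.5.2 is unstated and that the repeat of 10.3.3 under SAP 11 carries no information. It does not stand that the SAP requires one-hemisphere reads in 10.5.2, or that 19% of A16 scans enter with a different read. Both claims depend on leaving out the accuracy condition in SAP 7.2.1. Nor is there a read-level error in 10.5.3(2).

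A one-hemisphere repeat of the primary kappa, to give SAP 11 something to test, would gain nothing. It would put 16 one-sided reads among 242 − 16 = 226 whole-brain reads, mixing read units in the way the concern objects to, and neither document asks for it.

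**Conclusion.** No change follows. The open point in SAP 10.5.2 is a missing detail that an analyst with both documents would fill with whole-brain reads. If one-sided reads were used instead, one exploratory kappa would move by between −0.047 and +0.014 on average. That range rests on the assumed 5% to 20% rates and on the simulation model, not on data in the documents. No success criterion attaches to that kappa, and it is outside the success rule in SAP 10.2, which covers only the three primary analyses.

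The redundancy in SAP 11 is loose drafting. It biases nothing, and the section still does its work for 10.3.1 and 10.3.2, the only primary analyses in which SAC reads are one-sided. An identical kappa in that output reflects identical input and should not be cited as robustness. The primary kappa is defined on whole-brain reads in both protocol and SAP, and nothing here alters it.
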